Local IRB # 202006-003 IRBNet # 1599521

BUTLER HOSPITAL INSTITUTIONAL REVIEW BOARD

PROTOCOL

1.) Project

Title of Project: Effects of L-theanine on Motor Cortex Excitability in Healthy Subjects: A Paired-Pulse TMS

Study

Principal Investigator (PI): [name].

Other Investigator(s): [name].

2.) Description of Study

A. Specific Aims

To study the effects of a single dose of L-theanine (L- γ -glutamylethylamide or N⁵-ethyl-L-glutamine) on motor cortex excitability in healthy subjects, using paired-pulse transcranial magnetic stimulation (ppTMS) measures. The hypothesis is that L-theanine enhances motor cortex excitability in healthy subjects.

B. Background

L-theanine is the primary psychoactive component uniquely in green tea¹. Epidemiological studies support that green tea consumption is an independent factor associated with lower prevalence of depression²⁻⁴. Preclinical studies have demonstrated anti-depressant effect of L-theanine in rodents and provided evidences for its pharmacological properties of N-methyl-D-aspartate (NMDA) and gamma-aminobutyric acid (GABA) agonism⁵⁻ 7 . Yet these effects have not been proven in humans. Only one open-label clinical trial 8 has studied antidepressant effect of L-theanine in major depressive disorder, and suggested its effectiveness as an augmenting agent to an existing antidepressant regimen. Furthermore, the psychotropic properties and mechanism of L-theanine are to be elucidated. Paired-pulse transcranial magnetic stimulation (ppTMS) is a well-established technique to investigate frontal cortical excitability mediated by the inter-neuron NMDA and GABA receptors⁹. Several studies¹⁰⁻¹⁴ in subjects with MDD have demonstrated specific changes of ppTMS measures, including impaired short-term intracortical inhibition (SICI, mediated by GABA-A receptor and fast inhibitory postsynaptic potentials) and long-term intracortical inhibition (LICI, mediated by GABA-B receptor and slow inhibitory postsynaptic potentials) and intracortical facilitation (ICF, mediated by NMDA receptor and excitatory postsynaptic potentials), compared to healthy subjects. Treatment effects of MDD elicited by escitalopram corresponded with changes in these markers¹³. This is relevant to the study aim in that the motor cortex excitability is mediated by the glutamatergic system, and ppTMS offers an opportunity to investigate how L-theanine may manipulate the glutamatergic system in the frontal region by changing motor cortex excitability first in healthy subjects (phase 1, as described in this protocol). Then we plan to examine its potential as an augmenting agent for MDD in a placebo-controlled design (phase 2).

C. Experimental Method

C1. Brief Description of Subjects

Adults (N=10 completing all 3 visits) (>18 and <65 years old) without any neuropsychiatric disorders or contraindication to application of TMS will be recruited from the local community.

C2. Study Design

This is a double-blinded randomized order, cross-over, placebo-controlled trial to study the acute effects of a single dose of L-theanine on the motor cortex excitability, measured by paired-pulse TMS metrics.

1) Visit 1: The subject will sign consent form to enter the study; A clinical interview (SCID 5, for 30-45min) will be conducted by a SCID interview-trained clinician ([name]) to ensure the inclusion and exclusion criteria are met. Releases will be signed to obtain records that confirm eligibility from a medical standpoint.

Date most recently revised (11/17/2020)

Protocol Version (4)

- Eligible subject will then be instructed to refrain from any nutraceuticals or psychotropic medications for 7 days prior to visit 2. After medical clearance, the subject will be randomized to active or placebo pill.
- 2) On visit 2: the subject will receive the first session of ppTMS data collection procedures (see below for details). During this session measurement of cortical excitability happens before and after ingestion of a capsule (active L-theanine or placebo). The subject will be instructed to continue to refrain from any nutraceuticals or psychotropic medications until visit 3, which is scheduled within one week.
- 3) On visit 3: The subject will receive ppTMS data collection procedures that are identical to visit 2, before and 30min after drug administration. If the subject was given active L-theanine during visit 2, they will receive placebo during visit 3; if the subject was given placebo during visit 2, they will receive active L-theanine during visit 3. The PI and co-PI will still be blinded regarding the condition of the drug. Arrangements will be made for compensation and participation will conclude.

C3. Specific Procedures or Treatments

At both visits 2 and 3, all subjects will undergo a standard ppTMS protocol once before and again after administration of a single dose of active L-theanine or placebo. This protocol involves delivery of programed ppTMS stimuli (magnetic pulses) to the head over the motor cortex while measuring the resulting evoked motor potentials through surface electromyography (EMG) on the subject's hand.

MOTOR THRESHOLD DETERMINATION: EMG will be recorded from the right abductor pollicus brevis (APB; thumb) muscle in order to measure the amplitude of motor evoked potentials (EMG) recorded by LabChart software throughout the procedure. The subject will be seated comfortably, given earplugs, and instructed to maintain relaxed throughout the experiment. Sticky electrodes will be attached to the skin around the thumb and wrist of the subject's right hand. Single pulses of TMS will be applied to the area of the left motor cortex corresponding with right thumb muscle ABP (using with a Magstim figure-of-eight magnetic coil and Magstim stimulators) to determine the resting motor threshold (RMT), defined as the intensity that produces a MEP in relaxed APB muscle of > 50 uV during 5 of 10 trials. This value is used to calibrate the intensity of pulses for the ppTMS measures of cortical excitability.

PAIRED-PULSE TMS PROTOCOL: Paired pulses of TMS will subsequently be used to assess various measures of cortical excitability. For example, for intercortical facilitation (ICF) measurement, a subthreshold conditioning stimulus (CS) at 80% RMT precedes a suprathreshold testing stimulus (TS) at 120%RMT. Inter-stimulus intervals (ISIs) of different durations, e.g., 10 ms and 20 ms will be used. ICI will be tested with a suprathreshold CS at 120% of RMT followed by test stimulus at 120% of RMT. Again, trials will be repeated with at ISIs of different durations, e.g. 2, 5, 50, and 100ms.

Each ppTMS protocol will consist of 25 trials for each of the six conditioned stimuli in random order. MEP amplitudes will be recorded from each trial. SICI, ICF and LICI metrics are estimated from averages of the conditioned MEP amplitudes.

DRUG ADMINISTRATION: The subject will be dispensed a single dose of either drug or placebo as prepared by an unblinded pharmacist. The subject will take placebo or L-theanine 400mg of with water and remain sitting in a quiet room for relaxation for 30min, after which the ppTMS protocol will be repeated. The PI/co-PI and the subject will be blinded to the result of randomization.

SAFETY ASSESSMENTS: Prior to starting TMS procedures, the subject will be screened for TMS risk with a standard TMS Safety Screen questionnaire. Visual analog scales (e.g. sense of calm, anxiety level, sedation, irritability, level of fatigue), will be completed prior to and following each ppTMS protocol to evaluate effects of the stimulation as well as possible effects of L-theanine on mood. Verbal query will be used to elicit any other adverse effects. Subjects will be discharged from the research facility after each visit when it is clear they

are comfortable and suitable to drive home. The total estimated time for each visit is estimated to be 2.5 hours to 3 hours.

C4. Data Analysis

No previous studies have been done on the effects of L-theanine on intracortical facilitation or inhibition. However, many similar studies have been done with ppTMS to evaluate pharmacological effects of a drug on these same cortical excitability measures. Previous studies on the effects of NMDA receptor antagonists (dextromethorphan¹⁵, memantine¹⁶) on ICF and of GABA receptor agonist (benzodiazepine¹⁷) on ICI. Those studies had sample sizes that ranged from 8-10 healthy individuals. The estimated clinically meaningful effect size is 10% of change in the ICI and/or ICF. Thus, after consultation with [name] on sample size estimation, we plan to collect a full set of data from N=10 healthy subjects. The Pharmacy Department will participate in the process of L-theanine/placebo packing, storage, randomization and distribution.

SICI, ICF and LICI values were calculated by the ratio of conditioned MEP / unconditioned MEP. We used Wilcoxon signed-rank tests to compare the baseline-to-post-drug changes (Δ =post-drug value minus pre-drug value) of SICI, ICF and LICI between placebo and L-theanine conditions. Two-sided P value < 0.05 is considered statistically significant.

D. Material Inducements

Subjects will be compensated in the form of gift cards for their participation:

\$20 for participating in informed consent and initial SCID-5 interview;

\$50 for participating in the first session of placebo/L-theanine administration and ppTMS procedures; \$80 for participating in the second/last session of placebo/L-theanine administration and ppTMS procedures. Therefore, Subjects will be compensated in the form of gift cards for their participation as follows: \$20 for completion of visit 1; \$50 for completion of visit 2; and \$80 for completion of visit 3. They will be compensated \$150 in total if they completed the whole study.

E. Training of Research Personnel

The PI and co-principal investigator ([name]) have received SCID-5 training for clinical interview and will have TMS research credentials completed/documented by the Butler Neuromodulation Research Facility, per policy. The PIs have received CITI training program for conflict of interest in human subject research and good clinical practice, REDCap programming training for data management. A special ppTMS workshop with [name] from BIDMC is planned for technical training on the ppTMS protocol.

3) Human Subjects

A. Subject Population

We plan to enroll enough subjects to ensure N=10 subjects who meet inclusion criteria complete all 3 visits:

- 1) Adult, aged between 18 and 65 years old;
- 2) Able to read/speak English and give informed consent
- 3) No current or history of Axis I psychiatric disorders by DSM-5.
- 4) Free of psychotropic medication use

Exclusion Criteria:

- 1) History of significant acute or chronic neurological or medical disorder or condition that increases risk for seizure with TMS;
- 2) History of alcohol use disorder, nicotine dependence, adjustment disorder;
- 3) History of allergic reactions to L-theanine or green tea;
- 4) Pregnancy;
- 5) Unable/unwilling to abstain from nutraceutical supplements and psychotropic agents during participation in the study

- 6) Unable/ unwillingness to refrain from recreational substance use (e.g. alcohol or marijuana) during participation in the study;
- 7) Meet criteria for exclusion from TMS or MRI procedures, including intracranial metal implants or nonremovable ferromagnetic items in the head/neck.

B. Recruitment and Consent Procedures

Subjects will be recruited through media advertisement, including social media, flyers. Potential sources of subjects include the community, hospitals, schools, etc. Telephone screening will be used to explain the study and establish preliminary eligibility for those who express interest. Written informed consent will be obtained at the first visit, after describing the study in detail and answering all questions; if COVID-19 pandemic precautions preclude in-person evaluation, virtual screening and consent procedures will take place.

Given continued COVID-19 pandemic situation, we will implement video and phone session for the first visit. A "VERBAL CONSENT FOR USE OF E-MAIL AND VIDEOCONFERENCING IN A RESEARCH PROJECT" will be used. In this consent process, prospective subjects will be contacted by phone and informed of the consent proposal. They will be asked if they understand and agree to videoconferencing for evaluation and email communication for scheduling purposes. They will need to confirm if they have access to a computer, tablet, or smartphone with a built-in camera. The investigators will then follow the scripts described in the consent form word by word to the subjects. Risks (including confidentiality) and benefits (including reduced risk of exposure to COVID-19) will be reviewed.

At the end of the consent form, the investigator will sign and date to indicate that all the instructions have been followed and the subject gave informed consent.

C. Potential Risks

- 1. We acknowledge the risk of loss of confidentiality in the course of the study.
- 2. Potential risks from L-theanine administration

L-theanine is a generally safe nutraceutical agent. There are two clinical trials that studied patients with MDD⁸ (N=20) or schizophrenia/schizoaffective disorders¹⁸(N=52), and reported minimal side effects from 250mg-400mg daily dosing for 8 weeks. Hidese et al⁸ reported "1 patient reported slight sleepiness; 2 patients reported increased duration of sleep of up to 2 hours than usual; 2 patients reported increased dream activity. All tolerated the medication without drop-out". Ritsner et al¹⁸ reported "L-theanine did not produce any side effects". Studies^{29, 30} that administered a single dose of 250mg L-theanine before evaluating task electroencephalography (EEG) in healthy human subjects (N=13-15) reported no side effects. L-theanine was still tolerated well after two weeks of supplementing with doses nearly 60 times the usual amount used in animal studies. ^{19,20} Therefore, we anticipate minimal if any side effects from 400mg one-time dosing of L-theanine, as proposed in this study. Potential risks are limited to allergic reaction (extremely rare) and sleepiness/increased length of sleep or increased dream activity (rare).

3. Potential risks from ppTMS procedure

Headache (5%-10%)²¹, Scalp discomfort (5%-30%)²², dizziness or fainting episode, seizure, with an estimated risk of 0.003%²³ are the potential risks of high-frequency repetitive TMS delivered to the dorsolateral prefrontal cortex as a treatment modality. ppTMS (2 pulses each time) delivers a significantly lower amount of energy, which reduces the potential risks, but the ppTMS protocol pulses are delivered over the motor cortex, which could increase risk of seizure induction if given in high frequency trains. The ppTMS procedure does not delivery high frequency pulses and thus carries the same risks associated with a standard motor threshold procedure, which include scalp discomfort, hearing acuity damage, seizure. Single or paired-pulse TMS has an estimated risk of 2/100,000 of inducing seizure in low-risk healthy subjects (Rossi 2020, review manuscript).

D. Protection of the Subject

D1. Measures to Minimize Potential Risks

- 1. Minimize risks of loss of confidentiality: see D2.
- 2. Minimize potential risks from L-theanine:
 - 1) Clinical interview on visit 1 to ensure inclusion and exclusion criteria. Prevent subjects from exposure to L-theanine if there is a history of known allergic reaction.
 - 2) Observation for 1 hours after the administration of L-theanine (during ppTMS procedure and safety assessment after the procedure), to ensure that the subject has no sedation or other side effects.
- 3. Minimize potential risks from ppTMS procedure:
 - 1) Clinical interview at visit 1 to ensure inclusion and exclusion criteria.
 - 2) Medical clearance procedure and screening with TMS safety screen tools to prevent subjects from exposure to TMS if there is any increased risk of seizure.
 - 3) Comfortable positioning, ongoing direct monitoring of subject for adverse effects
 - 4) All TMS procedures will be conducted by PI/co-PI who are medical doctors and TMS-trained
 - 5) Ear plugs will be provided to subjects to prevent hearing damage.
 - 6) All procedures to be conducted in the BNRF, a specialized neuromodulation research facility at Butler with all-day coverage by TMS-trained physicians, emergency response buttons/protocols, etc. Subjects will also be monitored closely for dizziness, fainting or syncopal episode, and differentiate from seizure. Staff receive training in detection and management of seizure and syncope during neuromodulation procedures.

D2. Measures to Ensure Confidentiality

- 1. The clinical interview and medical clearance documents will be stored in a locked cabinet within the Butler Neuromodulation Research Facility (BNRF) facility, which is locked after hours and has limited keyed access for a small number of BNRF research staff.
- 2. All subjects will be assigned a study ID number upon enrollment and ID will be used for research data capture.
- 3. This study will use Care New England's instance of REDCap for the collection and storage of data. REDCap is a secure, web-based application developed by Vanderbilt University for building and managing surveys and databases. It is primarily designed to support online or offline data capture for research studies, quality improvement, and operations. Care New England's instance of REDCap is hosted within the Care New England data center in Warwick, RI. This REDCap instance is role-based and is fully integrated with CNE's Active Directory structure. It enjoys 24/7/365 enterprise-level support and security inherit to CNE's HIPAA-compliant data center. Network transmissions (data entry, survey submission, and web browsing) to and from REDCap are protected via TLS 1.2 encryption. REDCap's data is stored on encrypted servers within CNE's data center.

D3. Data Safety Monitoring Plan

We plan to establish a data monitoring panel with the PI ([name]) and co-PI ([name]), and several unaffiliated clinical researchers with relevant expertise. The group will review the study and its progress prior to initiation. The PI/co-PI will present all adverse effect data to the panel and report any other issues related to safety. Weekly meetings between [name], [name] (and any BNRF staff involved in the project) will be held to review progress and adverse events.

We plan to do an interim analysis as mentioned above to re-estimate sample size, when N=5 subjects have been enrolled. In cases of any adverse effects from TMS or L-theanine, a comprehensive evaluation of the severity of the effect (and reported to the Butler IRB if determined a reportable event per IRB guidelines) and if

the subjects wish to stay in the study they will be aware they have the opportunity to withdraw at any time of the study. When statistically significant differences are observed for the ppTMS measures (SICI, LICI, ICF) in a dose-dependent correlation with L-theanine, or there are no differences observed whatsoever, the study will be concluded.

E. Potential Benefits

The study will contribute valuable data to elucidate the effects of L-theanine on motor cortex excitability. If the study yields positive results, it could support a phase 2 study on the effects of L-theanine on motor cortex excitability in patients with MDD and establish the foundation of L-theanine as a potential augmenting agent for pharmacotherapy of MDD.

F. Risk-Benefit Ratio

The risk-benefit ratio is estimated to be minimal considering the significant benefit that could be potentially generated from the study, versus the very low risks of the two procedures as mentioned above, as well as the measures that will be taken to further minimize those risks.

4) REFERENCES

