5D. PHI is only needed for activities preparatory to research YES 🔀 NO	

6) DESCRIPTION OF PHI TO BE COLLECTED UNDER WAIVER

Name, age, sex, handedness, contact information, medical history, substance and nutraceutical use history. (Medical clearance documents to be requested from PCP will be obtained following signature on a separate CNE Authorization form)

7) ADVERTISEMENTS

The advertisement will be submitted as amendment if the protocol is approved.

8) RESRULTS INFORMATION

Primary results:

Compared to matching placebo, 400 mg single dose L-theanine elicited significantly higher post-pre drug change (Δ) of ICF (Mean±SE Δ ICF_{L-theanine}=0.073±0.073 vs. Δ ICF_{Placebo}=-0.341±0.176, p=0.016, Cohen's d = 1.02) and LICI (Mean±SE Δ LICI_{L-theanine}=0.145±0.100 vs. Δ LICI_{Placebo}=-0.068±0.053, p=0.037, Cohen's d = 0.91) within each individual. No significant difference was found for SICI (Δ SICI_{Placebo}= 0.005±0.060 vs. Δ SICI_{L-theanine}=0.059±0.028, p=0.450, Cohen's d = 0.35). L-theanine did not change unconditioned MEPs (or baseline rMT) differently than placebo (Table 1). No adverse effects from L-theanine were observed. The subjects were unable to guess the condition of drug (placebo vs L-theanine) after each session of experiment more accurately than random. (SE = standard error of the mean)

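### One inhibition setting, with both pulses at 120% RMT, covers intervals from 2 to 100 ms, so the short-interval ratio is not a clean measure of SICI, and the intervals behind each metric are not stated

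*Combined protocol and SAP*

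**What the plan says.** All places are in the combined protocol and SAP.

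- **2.B Background** presents SICI and LICI as distinct measures, linked to GABA-A and GABA-B receptors respectively. It attaches no intensity and no interval in milliseconds to either.
- **2.C3, Motor Threshold Determination** defines RMT as "the intensity that produces a MEP in relaxed APB muscle of > 50 uV during 5 of 10 trials". On the use of RMT it says: "This value is used to calibrate the intensity of pulses for the ppTMS measures of cortical excitability".
- **2.C3, Paired-Pulse TMS Protocol** describes ICF as a design in which "a subthreshold conditioning stimulus (CS) at 80% RMT precedes a suprathreshold testing stimulus (TS) at 120%RMT", with 10 and 20 ms as example intervals. For inhibition: "ICI will be tested with a suprathreshold CS at 120% of RMT followed by test stimulus at 120% of RMT", with 2, 5, 50 and 100 ms as example intervals. On volume: "Each ppTMS protocol will consist of 25 trials for each of the six conditioned stimuli in random order". On the metrics: "SICI, ICF and LICI metrics are estimated from averages of the conditioned MEP amplitudes".
- **2.C4 Data Analysis** gives a different description of the metrics: "SICI, ICF and LICI values were calculated by the ratio of conditioned MEP / unconditioned MEP". The endpoint is the post-drug minus pre-drug change in each ratio, compared within subject.
- **8 Results Information** reports SICI and LICI separately. For SICI the mean change is 0.005 on placebo and 0.059 on L-theanine (p=0.450). It also compares unconditioned MEPs between conditions, citing a Table 1 that is not in the text available to me.

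**The concern.** A paired-pulse inhibition ratio is meant to show how far a first pulse suppresses the response to a second. That reading needs a measured amplitude that belongs to the second pulse. With the first pulse above threshold and only 2 or 5 ms ahead, the amplitude may contain the first pulse's own response. The one inhibition setting in the plan produces this situation at its two short example intervals.

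At stake is the meaning of the SICI result. Section 8 itself only reports no significant difference, but section 2.B ties SICI to GABA-A, so a reader will naturally take p=0.450 as a statement about that pathway. Because intervals are not assigned to metrics, a reader also cannot tell whether any other metric includes the short-interval pairs.

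A smaller matter lies beside this. Sections 2.C3 and 2.C4 describe the metrics differently, and the source and number of the unconditioned MEPs in the denominator are not stated.

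**Working it through.** **1. The plan's count.** Example intervals: 2 for ICF (10, 20 ms) plus 4 for inhibition (2, 5, 50, 100 ms) = 6, which matches the six conditioned stimuli. At 25 trials each that is 6 × 25 = 150 conditioned trials per block. If the examples were used, 2 × 25 = 50 of them are the 2 and 5 ms pairs. No other setting for a short interval appears in the text.

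**2. Does the conditioning pulse evoke a response?** By definition, 100% RMT gives a response in 5 of 10 trials, or 50%. Provided that response probability does not fall as intensity rises, 120% RMT gives at least about 50%. Both pulses have the same intensity, so the first response should on average be as large as an unconditioned one at 120% RMT. The ICF conditioning pulse (80% RMT) is below threshold, so this does not arise there.

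**3. Do the responses overlap?** Let D be the MEP duration (not in the documents; assumed) and let both responses have the same latency. They overlap when D > ISI, and the overlapping share is max(0, (D − ISI)/D).

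| ISI | D = 5 ms | D = 10 ms | D = 20 ms |
|---|---|---|---|
| 2 ms | 60% | 80% | 90% |
| 5 ms | 0% | 50% | 75% |
| 50, 100 ms | 0% | 0% | 0% |

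So when the first pulse evokes a response, overlap at 2 ms is certain for any D above 2 ms. At 5 ms it needs D above 5 ms.

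**4. What happens to the change?** The endpoint is a change, so I looked at changes rather than levels. Model: y(t) = f(t) + s·f(t − ISI), where f is a biphasic wave of duration D and s is the true ratio. The reading is the peak-to-peak of y from ISI to ISI + D, divided by the peak-to-peak of f. Take a true change from s = 0.4 to s = 0.6, which is 0.200. The reading at 0.6 minus the reading at 0.4 is shown below (single-cycle sine / Hann-windowed sine):

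| ISI | D = 5 ms | D = 10 ms | D = 20 ms |
|---|---|---|---|
| 2 ms | −0.046 / −0.042 | 0.129 / 0.068 | 0.182 / 0.165 |
| 5 ms | 0.200 / 0.200 | 0.000 / 0.061 | 0.089 / 0.010 |
| 50 ms | 0.200 / 0.200 | 0.200 / 0.200 | 0.200 / 0.200 |

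The distortion ranges from none (5 ms with a 5 ms MEP) or almost none (2 ms with a 20 ms MEP) to flat or reversed. Waveform, D, linear summation, equal latency, equal response size and the reading window are all assumptions. Trials in which the first pulse evokes nothing are read cleanly and would dilute the effect. The table shows only that the size and sign of the distortion cannot be settled from the documents.

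**5. The two metric descriptions side by side.** Section 2.C3 speaks of averages of conditioned amplitudes and names no denominator. Section 2.C4 divides by the unconditioned MEP. They are compatible if the first describes only the numerator, but the text does not say so. The single pulses described in 2.C3 serve to find RMT, whose stated use is to calibrate intensity. They are not named as the denominator.

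**The case against.** The strongest reply is that section 2.C3 is illustrative. The ICF setting and all the intervals are introduced as examples, and the procedure is called standard. A different setting may have been used at 2 and 5 ms. That stands, and it makes the limit on SICI conditional. It does not remove the problem, because the inhibition setting itself is stated flatly and is the only one given.

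A second reply is that the words short-term and long-term in section 2.B imply the mapping. That is a reasonable inference, but no interval is attached to either term, and no rule says whether intervals are averaged or one is chosen. The same gap applies to the two ICF intervals.

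A third reply is that a within-subject change cancels a constant distortion. This is partly right: under some assumptions in step 4 the change survives almost intact. Under others it vanishes or changes sign, so cancellation cannot be relied on.

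Two stronger readings are tempting and are not supported. A reader might infer from the six filled slots that no test-alone trials were run. Section 2.C3 counts only conditioned stimuli and so is silent on unconditioned ones, while section 8 shows that unconditioned MEPs were obtained. A reader might also infer that the unstated denominator biases the results or calls for discounting the reported p-values. Nothing in the documents shows that.

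**Conclusion.** The point holds in conditional form. As written, the plan applies a conditioning pulse that should evoke its own MEP at intervals short enough for that MEP to overlap the test response. If that setting was used at 2 or 5 ms, the short-interval ratio, and to an unknown degree its pre-to-post change, is not a clean measure of short-interval inhibition. The SICI result (p=0.450) is then uninformative about SICI or GABA-A in either direction; it is not shown to be wrong.

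If the intervals follow the names, one of three endpoints is affected. Because the mapping is unstated, LICI cannot be cleared by its label. A metric built only from the 50 and 100 ms pairs is unaffected (assuming that an MEP lasts less than 50 ms), and so is ICF with its 80% RMT conditioning pulse. The conclusion rests on the RMT definition, on response probability not falling between 100% and 120% RMT, and on an MEP longer than 2 ms (or 5 ms for the 5 ms pairs).

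The denominator's source and count, and the difference between sections 2.C3 and 2.C4, are matters of clarification only.

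**What to change.** - Reconcile sections 2.B and 2.C3 on the setting used for the short intervals, and state what was actually used. The choice of setting is the investigators'.
- State which intervals, and what averaging, form SICI, LICI and ICF.
- If 120% RMT conditioning was used at 2 or 5 ms, do not present the null SICI result in section 8 as evidence about SICI or GABA-A. Apply the same limit to any other metric that includes those intervals. If another setting was used, stating it removes this limit.
- As a clarification, keep the section 2.C4 ratio as the definition, reword the averages sentence in 2.C3 to describe the numerator, and give the source and number of unconditioned MEPs in each pre- and post-capsule block.

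The cost is a few sentences in sections 2.B, 2.C3, 2.C4 and 8. No new pulses, visits, subjects or re-analysis are needed.

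### About 82% of the mean ICF contrast is the fall in the placebo session, and pre-dose ICF is neither adjusted for in C4 nor given in section 8

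*Combined protocol and SAP*

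**What the plan says.** The Specific Aims state the direction expected: "The hypothesis is that L-theanine enhances motor cortex excitability in healthy subjects". Under C2 and C3, each subject attends two dosing visits in randomized, blinded order. At each visit a ppTMS block is recorded before dosing. The subject then takes the capsule and must "remain sitting in a quiet room for relaxation for 30min, after which the ppTMS protocol will be repeated".

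The C4 analysis uses Wilcoxon signed-rank tests to "compare the baseline-to-post-drug changes (Δ =post-drug value minus pre-drug value) of SICI, ICF and LICI between placebo and L-theanine conditions". The criterion is "Two-sided P value < 0.05 is considered statistically significant". C4 includes no adjustment for the pre-dose ratio and no comparison of pre-dose ratios between visits.

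Section 8 reports for ICF "Mean±SE Δ ICF_{L-theanine}=0.073±0.073 vs. Δ ICF_{Placebo}=-0.341±0.176, p=0.016", with a Cohen's d of 1.02, and defines the spread as "SE = standard error of the mean". It gives changes only. The table it cites is not in the available text and is cited only for unconditioned MEPs and baseline motor threshold.

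**The concern.** The aim concerns an increase in excitability after L-theanine. The ICF finding has a different shape: little movement in the L-theanine session and a larger fall in the placebo session. Two explanations fit those means. Quiet rest and repeat testing may lower ICF at both visits, with L-theanine offsetting the fall. Or pre-dose ICF may by chance have been higher at the placebo visits and then drifted back. A raw change score subtracts the pre-dose value in full, so the second mechanism would push the contrast in the drug's favour.

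Section E says positive results could support a phase 2 study in MDD, so it matters how firmly the ICF result stands. The measurements needed to look into this have already been taken.

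**Working it through.** **Inputs.** From section 8: ICF change +0.073 (SE 0.073) on L-theanine and -0.341 (SE 0.176) on placebo; LICI change +0.145 and -0.068; SICI change +0.059 and +0.005. From C4: planned n = 10. Section 8 does not state the number analysed, so n = 10 is an assumption below.

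**The plan's own effect size.** SD = SE × √n.
- At n = 10 the SDs are 0.231 and 0.557, their root mean square is 0.426, and d = 0.414/0.426 = 0.97.
- At n = 9 the same formula gives 1.02, the reported value.
- A paired d of 1.02 at n = 10 would need a correlation of about 0.77 between the two changes.

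The variant of d and the n are not stated, so the figure cannot be reproduced uniquely. Nothing below depends on it.

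**Share of the contrast.**
- ICF: 0.073 - (-0.341) = 0.414. Placebo share 0.341/0.414 = 82%; L-theanine share 0.073/0.414 = 18%.
- LICI: 0.145 + 0.068 = 0.213. Placebo share 0.068/0.213 = 32%.
- SICI: the placebo mean did not fall.

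**Each session alone, n = 10, t(9) = 2.262.**
- L-theanine: 0.073 ± 2.262 × 0.073 = 0.073 ± 0.165, i.e. -0.09 to +0.24 (p about 0.34).
- Placebo: -0.341 ± 2.262 × 0.176 = -0.341 ± 0.398, i.e. -0.74 to +0.06 (p about 0.085).

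**How a pre-dose difference enters.** Write D for the L-theanine-minus-placebo difference in a ratio. The change contrast is D_post - D_pre = 0.414. With slope b of D_post on D_pre, the adjusted effect is D_post - b × D_pre = 0.414 + (1 - b) × D_pre. Neither D_pre nor b is in the documents, so only a range can be shown:

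| Assumed D_pre | b = 0 | b = 0.5 | b = 1 |
|---|---|---|---|
| 0 | 0.414 | 0.414 | 0.414 |
| -0.2 | 0.214 | 0.314 | 0.414 |
| -0.341 | 0.073 | 0.243 | 0.414 |

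A positive D_pre moves the estimate the other way: at D_pre = +0.2 and b = 0.5, 0.414 + 0.5 × 0.2 = 0.514.

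**Precision.** Let D_pre and D_post have equal variance σ² across subjects and correlation r. The change contrast has variance 2σ²(1 - r) and the adjusted residual σ²(1 - r²). The ratio is (1 + r)/2, i.e. 0.65, 0.75 and 0.85 at r = 0.3, 0.5 and 0.7.

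Simulated power (n = 10, normal data, true effect 0.9σ; repeat runs agree to within about 2 points):

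| r (assumed) | Planned Wilcoxon | Adjusted intercept test |
|---|---|---|
| 0.3 | 57% | 70% |
| 0.5 | 71% | 78% |
| 0.7 | 89% | 91% |

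**Type I error.** With no drug effect and no condition on baseline, both tests reject about 5% of the time. Given a chance pre-dose difference of 2 SE, the Wilcoxon test on changes rejects about 14% at r = 0.3 and 9% at r = 0.7, against about 5% for the adjusted test. At 1 SE the Wilcoxon test stays at 4% to 5%.

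**The case against.** The strongest reply is that subtracting the placebo-session change is the purpose of the design. Order is randomized, subject and investigators are blinded, and both visits have the same procedures and the same rest. Under those conditions the change contrast is unbiased on average, and its p-value already allows for chance pre-dose differences. This stands: the planned test is not invalid.

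A reader might infer from the 82% share that pre-dose ICF was in fact high at the placebo visits, or that the contrast cannot distinguish a drug effect at all. The documents do not support either. A fall common to both sessions that the drug offsets gives the same means with no imbalance. The 9% to 14% rejection rates apply only given a 2 SE imbalance, which arises about 5% of the time by chance and is not shown anywhere. The larger placebo SE does not settle it, since extreme post-dose values or varied responses to rest would produce it too.

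It is also fair to say that section 8 prints both session means and does not claim that ICF rose on L-theanine. A rank test is a defensible choice for MEP ratios at n = 10, and replacing the stated test once results are known would be post hoc.

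These points limit the concern without removing it. Validity on average does not show whether this one small sample was balanced, and the pre-dose values that would show it are not in the available text.

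**Conclusion.** The concern holds in a limited form. About 82% of the mean ICF contrast is the placebo-session fall. The L-theanine session alone shows no clear rise (+0.073, 95% CI about -0.09 to +0.24 if n = 10). Because C4 does not adjust for the pre-dose value and section 8 does not report it, a chance imbalance between visits is not excluded. Its possible effect on the estimate ranges from none to most of the 0.414, depending on two quantities that the documents do not give.

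The raw change also gives up precision: about 13 points of power at r = 0.3, 7 at r = 0.5 and 2 at r = 0.7. Those figures assume normal data, equal pre and post variances, n = 10 and the stated r. The 82% is a ratio of means with a wide placebo interval, whereas the reported test is rank-based, so the share describes the result and is not itself a test of it.

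**What to change.** **In C4**, add a baseline-adjusted analysis for each of ICF, LICI and SICI. For each subject, take the L-theanine-minus-placebo difference in the post-dose ratio and regress it on the same difference in the pre-dose ratio. Test the intercept, which is the effect at zero pre-dose difference.

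State that the predictor is not mean-centred. With centring, the intercept becomes the unadjusted mean post-dose difference. If its standard error is still taken from the regression, the test rejects up to about 14% under no effect, and about 40% with a 2 SE imbalance, both at r = 0.7.

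As results are already reported, label this analysis post hoc and show it beside the planned Wilcoxon result, which stays as the stated test.

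**In section 8**, give mean pre-dose and post-dose ICF, LICI and SICI by condition, and state the number analysed. Do not interpret the ICF result as a rise on L-theanine; the reported means show a fall after placebo and no fall after L-theanine.

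**Cost.** A re-run on data in hand, one degree of freedom, a linear-model assumption at n = 10, and a possibly less favourable ICF result.
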